### **11.2. Recruitment and Informed Consent**

Patients will be sent or given a covering letter and patient information sheet describing the trial, and will be seen by one of the research team on the delegation log. The trial will be discussed with the patient, and after opportunity for questions, a delegated and trained member of the research team will seek consent. The time between giving the information and taking consent may be on the same day and all steps will be taken to ensure that patients are afforded a reasonable time frame to consider the trial and have had all their questions answered prior to consent.

Recruitment will continue until the target sample size is randomised. Patients who decline to participate in this trial will continue to receive care within the department as per standard care.

Written consent for the trial must be taken within 6 weeks prior to randomisation. The original, signed consent form will be retained in the Investigator Site File, with a copy filed in the clinical notes and a copy given to the patient.

A screening log will be kept to document details of all patients invited to participate in the trial, their reasons (if given) for not consenting, or not being randomised will be recorded (e.g. not meeting eligibility criteria for the trial).

### **11.3. Eligibility check**

Following consent, the Principal Investigator or a sub-Investigator on the delegation log will confirm the patient's eligibility prior to randomisation.

### **11.4. Screen Failures**

Following consent, patients who do not meet trial eligibility criteria prior to randomisation will be considered a 'screen failure' and withdrawn from the trial with no further data collected. Screen failure patients may be approached to participate in an observational registry at participating centres.

### **11.5. Randomisation**

Randomisation will be performed using a minimisation scheme to ensure patients randomised to each group are comparable at baseline. The minimisation scheme will account for a planned 6 cycle adjuvant chemotherapy regimen (Epirubicin and Cyclophosphamide (EC) or Fluorouracil, Epirubicin and Cyclophosphamide (FEC)), and HER2 (human epidermal growth factor receptor 2) status (positive or negative).

Eligible patients will be randomised by delegated and trained members of the research team at each centre using a 24-hour, central, secure, web-based randomisation system with concealed allocation.

Eligible patients will be randomised in a 1:1 ratio to receive standard care plus enalapril maleate (intervention under study) or standard care (control arm/standard care).

Randomisation system web address:

<https://www.sealedenvelope.com/access/>

This system is available 24 hours a day, 7 days a week.

In the event that the randomisation system is not accessible, the team should contact NCTU staff in normal working hours:

Email: [[contact]](mailto:[contact])

[contact]

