## 7. Introduction

### 7.1. Background

Breast cancer is the most common malignancy among women worldwide, with over 50,000 new UK cases every year. Treatment commonly includes surgery, anthracycline-based chemotherapy and radiotherapy, and is highly effective. However, anthracyclines can cause immediate, irreversible, damage to cardiac cells and, ultimately, impaired cardiac function and heart failure.

Anthracyclines, including epirubicin, are administered in an outpatient setting and are usually well tolerated. However, they have a dose-dependent toxic effect on the heart which can result in heart failure often only evident years after exposure. The long-term incidence is approximately 5%; this may be higher in older patients. Asymptomatic left ventricular systolic dysfunction (LVSD) is more common, evident in 9.7% of patients with breast cancer within 12 months. LVSD affects cardiac prognosis and limits subsequent cancer treatment options, particularly those that target the HER2 pathway such as trastuzumab (Herceptin). Waiting until anthracycline-induced heart failure becomes clinically evident is ill-advised. Response to treatment is poor and survival at 2 years is 40%; considerably worse than other causes of heart failure and for breast cancer itself.

The burden of cardiotoxicity is particularly important in a patient group in whom 78% will be alive 10-years following their cancer diagnosis. Preventing cardiac damage would offer clear benefits to patients and substantial costs savings to the NHS.

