## 17. Statistics

### 17.1. Sample Size

Audit data from 36 patients and 143 samples, showed a positive troponin T in 47% of patients who received  $>300\text{mg/m}^2$  of anthracycline in a six-cycle regimen. As a sensitive marker of cardiac cell death, we expect troponin to be “turned off” if enalapril is effective. There are other potential causes of an elevated troponin during chemotherapy that are accounted for in the sample size calculation. There is clinical consensus that a rate of 20% in elevated troponin would fully account for other causes such as infection.

Assuming alpha of 5%, and 90% power, 140 patients are needed to detect a reduction in the proportion of patients with cardiac troponin T present from 47% to 20% using a two-sided Fisher's exact test.

There is consensus within the clinical community that, a large effect size will be necessary to convince the clinical community to change the pathway of care for these patients.

Allowing for attrition, the trial will recruit and randomise 170 patients.

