### 17.1. Statistical Analysis

Data cleaning and analysis will be provided by staff within NCTU and Durham University. Primary analysis will follow intention to treat principles with patient data analysed according to randomisation and irrespective of intervention received; other analysis groups such as per-protocol may be considered subsequently. Every effort will be made to retain and include all patients who are part of the trial.

A full statistical analysis plan (SAP) will be developed for the outcome measures and agreed with the IDMEC and Chief Investigator prior to any analysis being undertaken.

Outcome data will be analysed at the end of the study, no interim analyses is planned.

The primary analysis of presence or absence of cardiac troponin T will be assessed using Fisher's exact test. Analysis of the secondary endpoints will be dependent upon the nature of the specific endpoint and data structure; global longitudinal strain (GLS) and left ventricular ejection fraction (LVEF) will be analysed as a change from baseline using a t-test to compare intervention and control groups.

Cardiac troponin I data will also be analysed using Fisher's exact test. Changes in cardiac troponin T and I will also be analysed as a continuous variable. Additional analysis of the primary endpoint will be performed using logistic regression to account for baseline factors (regimen and HER2 status). Adverse events data will be analysed using cross-tabulation. Sensitivity analysis will also be performed for adherence to the protocol.

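### Allocation is minimised on regimen and HER2 status, but the named secondary tests ignore both; if regimen predicts these outcomes, some precision and power is lost

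*Combined protocol and SAP*

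**What the plan says.** Section 11.5 allocates 1:1 by minimisation. It says that "The minimisation scheme will account for a planned 6 cycle adjuvant chemotherapy regimen" (EC or FEC), and it adds HER2 status (positive or negative) as the second factor. Centre is not a factor, and no random element is described.

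Section 17.1 (Statistical Analysis) brings the two factors into one analysis only: "Additional analysis of the primary endpoint will be performed using logistic regression to account for baseline factors (regimen and HER2 status". For the secondary outcomes:

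- GLS and LVEF: the measures "will be analysed as a change from baseline using a t-test to compare intervention and control groups".
- Troponin I: "Cardiac troponin I data will also be analysed using Fisher's exact test".
- Continuous troponin T and I: an analysis is announced, but no model or covariates are named.

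The same section says that secondary analyses will depend on the endpoint and the data structure, and that a full SAP will be agreed before any analysis. The text available here contains no such SAP.

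Two other places bear on whether regimen is prognostic. Section 7.1 says of anthracyclines that "they have a dose-dependent toxic effect on the heart". Section 15.1 permits two regimens, with planned epirubicin of 6 × 75 = 450 mg/m² (FEC 75) and 6 × 90 = 540 mg/m² (EC 90).

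**The concern.** Minimisation keeps the arms alike on regimen and HER2 status, so differences between patients on those factors contribute almost nothing to the treatment difference. A test that ignores the factors still counts that variation in its standard error. If the factors predict the outcome, the standard error is larger than the allocation method warrants: intervals are too wide, p-values too large and real differences easier to miss.

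GLS, LVEF and troponin I carry the trial's cardiac-function and corroborating evidence. The sample size rests on the primary endpoint alone, so no power was set aside for them. The plan is also uneven: the factors were thought important enough to balance on and to adjust for in a model of the primary endpoint, but they are not carried to the secondary comparisons.

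**Working it through.** **The plan's own figure.** Section 17.1 (Sample Size) states "Assuming alpha of 5%, and 90% power, 140 patients are needed" for a fall "from 47% to 20% using a two-sided Fisher's exact test". With p1 = 0.47, p2 = 0.20 and mean 0.335, the uncorrected size per arm is

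n = [1.960·√(2 × 0.335 × 0.665) + 1.282·√(0.47 × 0.53 + 0.20 × 0.80)]² / 0.27² = 62.1, so 63 per arm (126 in total).

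The continuity correction, (n/4)·[1 + √(1 + 4/(0.27n))]², gives 69.3, so 70 per arm, or 140. Enumerating the two-sided Fisher test at 70 per arm gives 90.8% power. The figure of 140 is reproduced, and nothing below alters it.

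**GLS and LVEF: size of the unadjusted t-test.** Let R² be the share of outcome variance that regimen and HER2 status explain together. With both factors balanced:

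- true two-sided size = 2·Φ(−1.96/√(1 − R²))
- unadjusted interval width relative to adjusted = 1/√(1 − R²)
- equivalent sample size for 140 patients after adjustment = 140/(1 − R²)

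Example at R² = 0.05: 1.96/√0.95 = 2.011, size 4.4%; 1/√0.95 = 1.026; 140/0.95 = 147.4.

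The documents give no R², so a range is shown. The theory was checked with 12,000 null simulations per setting at N = 140. Assumptions that are not in the documents: half the patients on each regimen, 15% HER2 positive, R² split equally between the two factors, and a probability of 0.8 or 1.0 of assigning the arm that minimisation favours.

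| R² | Size, theory | Size, simulated | Interval too wide by | Adjustment worth, in patients |
|---|---|---|---|---|
| 0 | 5.0% | 4.9–5.2% | 0% | 0 |
| 0.02 | 4.8% | 4.7% | 1.0% | about 3 |
| 0.05 | 4.4% | 4.4–4.6% | 2.6% | about 7 |
| 0.10 | 3.9% | 3.7–4.0% | 5.4% | about 16 |

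A linear model with both factors had a simulated size of 4.7–5.4% throughout. With 170 randomised and 17.6% missing at random (30/170, the loss that takes 170 to 140), the unadjusted size was 4.4% at R² = 0.05 and 4.0% at R² = 0.10, so the picture is the same.

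**What these R² values require.** If regimen alone carries the effect and the split is 50/50, R² = 0.25 × (gap in total SDs)², so the gap is 2√R²: 0.28, 0.45 and 0.63 SD for R² of 0.02, 0.05 and 0.10. A 0.2 SD gap gives R² = 0.01, size 4.9% and intervals 0.5% too wide. An 80/20 split with a 0.3 SD gap gives R² = 0.16 × 0.09 = 0.014 and size 4.8%.

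**Troponin I: Fisher's exact test.** With no covariate effect, the exact size at 70 per arm is 3.1% at an event rate of 20% and 3.4% at 47%. Discreteness alone therefore costs 1.6–1.9 points. Simulated sizes, with the same odds ratio for each factor:

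| Odds ratio | Minimisation | Simple randomisation |
|---|---|---|
| 1 | 3.4–4.0% | 4.2–4.3% |
| 2 | 3.3–3.5% | 3.9–4.0% |
| 3 | 2.9% | 3.9–4.2% |

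At odds ratio 1 the factors do nothing, yet the columns still differ by 0.3–0.8 points, so the gaps below that row cannot all be credited to balancing prognostic factors. A cleaner comparison used 20,000 runs and event rates of 20% and 40% by regimen (odds ratio 0.667/0.25 = 2.7). Size was 3.9% under simple randomisation and 3.3% under minimisation, and 4.0% under both when regimen had no effect. There, minimisation accounts for 0.6 of a 1.7-point shortfall. Overall its part is about 0.5 to 1 point at odds ratios of 2–3.

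**The case against.** The strongest reply is that the loss is conditional, probably small and always in the safe direction. The documents support a dose effect in general, not its size between 450 and 540 mg/m². R² = 0.05 needs a regimen gap of 0.45 SD from a 20% difference in dose (540/450 = 1.2), which is a lot to expect. The documents give no evidence that HER2 status predicts these outcomes. Herceptin planned within four weeks of the anthracycline is an exclusion, and the final echocardiogram must precede Herceptin. An SAP is also still to come and may add adjusted analyses. All of this stands, except that a future SAP does not cancel the tests already named.

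Three stronger readings are tempting but not supported:

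- **That the intervals are too wide and the error rate is below 5% as a matter of fact.** At R² = 0 the t-test has its nominal size, and no document gives an R².
- **That minimisation explains the conservatism for troponin I.** Most of it would be there without minimisation. Only a test is named, so there is no planned interval to be too wide.
- **That stratifying troponin I buys a known gain in power.** In one assumed scenario (about 30% v 12%) power is 70% for Fisher's test and 76% for a stratified Mantel-Haenszel test, but that contrast mixes a change of test with stratification.

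**Conclusion.** The point holds in conditional form. The named secondary tests do not use the factors that govern allocation. To the extent that those factors predict GLS or LVEF change, the t-test is conservative: over an assumed R² of 0 to 0.10, size runs from 5.0% to 3.9% and intervals are 0 to 5.4% too wide. At R² of 0.01–0.05, the more plausible range, the loss is small: size 4.9–4.4% and intervals 0.5–2.6% too wide. The protocol's own account supports regimen as prognostic; including HER2 rests on the convention of analysing by the allocation factors. For troponin I the part due to minimisation is secondary to the discreteness of Fisher's test.

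There is no bias and no excess of false positives, and neither the primary result nor the sample size is affected. This is an improvement available at almost no cost, not a flaw that threatens the conclusions.

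**What to change.** In section 17.1 (Statistical Analysis), or in the SAP before any analysis, state that the secondary comparisons include both minimisation factors as recorded at randomisation:

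- **GLS, LVEF and continuous troponin T and I:** a linear model with treatment, planned regimen and HER2 status, reporting the adjusted difference and its interval.
- **Troponin I, present or absent:** a Mantel-Haenszel test and risk difference stratified by regimen and HER2 status, or logistic regression adjusted for both.
- **Unadjusted t-tests and Fisher's test:** keep as supportive analyses.

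The cost is a sentence or two of text. Both factors are already held for every randomised patient, and the linear model gives up two degrees of freedom. If the factors turn out not to matter, the interval width is essentially unchanged (simulated ratio 0.9995 at R² = 0). The targets of 140 evaluable and 170 randomised stay as they are. Fixing this in advance matters because adjustment chosen after the data are seen would be open to challenge.

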#### **11.6. Blinding**

The trial will employ a prospective randomised blinded endpoint design; analysis of troponin I and troponin T will be completed by laboratory staff who are blinded to the patients' trial allocation, as detailed in the trial PROACT laboratory manual.

All echocardiograms will be sent to an independent Core laboratory for assessment by a BSE accredited echocardiographer/or an advanced trainee or consultant cardiologist blind to the intervention.

#### **11.7. Un-blinding**

This is an open label trial and, as such, no un-blinding procedures are specified in this trial.

#### **11.8. Informing General Practitioners of Patient Participation**

Following explicit consent of the patient, General Practitioners will be informed of their patient's decision to participate and their randomisation status. A letter providing information about the study and inviting GPs to contact the investigators if they have questions will be sent following consent.

## 12. Adherence and Withdrawal

### 12.1. Assessment of adherence

Study visits have been planned to coincide with routine clinical practice where possible to enable adherence to the trial procedures.

Adherence with trial medication will be monitored and recorded throughout the trial for patients randomised to receive the trial intervention; enalapril maleate.

### 12.2. Withdrawal of participants

Patients may withdraw from the trial at any time if they wish to, without giving reason and without any adverse consequences for their ongoing clinical management. Patients in the intervention arm will need to stop taking enalapril maleate on the day they withdraw, and return all unused drug to the clinical research team.

All patients will be made aware of their right to withdraw from the study, and this information will be included in the patient information sheet.

Patients should be withdrawn from the trial by the clinical team if:

- the patient suffers unacceptable side effects caused by enalapril maleate;
- the patient becomes ineligible between randomisation and commencement of chemotherapy;
- the patient becomes pregnant or there is evidence that a patient fails to use adequate birth control;
- the patient has disease recurrence.

Data and blood samples for troponin assessment collected up to the point of withdrawal will be kept and used in the analysis of the trial.

Patients will be asked upon withdrawal:

- whether further data can continue to be collected from their medical records;
- whether samples collected for future research may still be analysed;
- whether they may be approached in future research connected to the trial.

This information will be captured on a withdrawal form, to be stored in the ISF and a copy of which sent to NCTU (by email), this will also be captured in the eCRF.

Data from patients who withdraw will remain in the overall analysis; however, dependent on the stage of withdrawal, then further patients may be recruited to ensure that the sample size is reached.

## 13. Trial Procedures

### 13.1. Summary of Trial Assessments

	Baseline (up to 6 weeks prior to randomisa- tion)	Day 1 (at least 5 days prior to Cycle 1 Day 1)	Dose evaluation visit 1	Dose evaluation visit 2	Dose evaluation visit 3	Cycle 1, Day 1	Cycle 2, Day 1	Cycle 3, Day 1	Cycle 4, Day 1	Cycle 5, Day 1	Cycle 6, Day 1	Trial Completi- on Visit b)
Consent a)	X											
Demographics	X											
Medical History	X											
Cancer history	X											
Performance Status	X											
NYHA Class	X											
Concomitant medications b)	X	X	X	X	X	X	X	X	X	X	X	X
Physical Assessment (height and weight)	X											
Blood Pressure	X		X	X	X	X	X c)	X				
Troponin T	X d)						X c)	X				
Troponin I	X						X c)	X				
U+Es	X		X	X	X		X c)	X				
eGFR	X											
Pregnancy test e)	X											
Echocardiogram f)	X											X
Eligibility check	X											
Randomisation	X											
Enalapril (intervention group only)		X	X	X	X	X	X	X	X	X	X	
Adherence to enalapril (intervention group only)		X	X	X	X	X	X	X	X	X	X	X
Standard care adjuvant chemotherapy (all patients)						X	X	X	X	X	X	
Adverse Events		X	X	X	X	X	X	X	X	X	X	X
Buccal swab for future research	X											
Blood sample for future research	X							X		X		X
Acceptability of trial interventions assessment									X			X

- a) Consent must be taken prior to baseline assessments and confirmation of eligibility, and within 6 weeks of randomisation.
- b) A list of all medication currently being taken by the patient, including total daily dose, should be recorded at baseline; changes and new medications must be recorded throughout the trial.
- c) All blood samples, including those for troponin T and I, MUST be taken before the next dose of chemotherapy is given; these and blood pressure monitoring can be performed up to 72 hours in advance of the day of chemotherapy.
- d) Troponin T at baseline will be used to assess eligibility
- e) Women between the ages of 18 and 50 must have a negative pregnancy test at baseline, and prior to randomisation and use adequate contraception from consent, throughout the trial.
- f) A Transthoracic Echocardiogram (TTE) must be performed at baseline. At the time of the TTE, blood pressure and heart rate should be measured, and recorded. A TTE will also be performed following the end of chemotherapy. Patients planned to receive Herceptin, must have their TTE performed prior to starting this. All TTEs must be transferred to the Core laboratory for analysis as part of the trial.
- g) Four weeks following the last dose of epirubicin.

## 13.2. Assessments

In addition to standard care procedures, a number of baseline assessments will take place prior to randomisation. Where routine assessments are the same as trial assessments for eligibility, and performed following consent to the trial, these will be used to assess eligibility for PROACT. These may include:

- Medical and cancer history
- Demographics
- U&Es
- Pregnancy test

If these aren't done routinely at that time-point, they will need assessment as part of the trial.

### 13.2.1. Demographic Information

The following demographic data will be recorded as part of the trial at baseline:

- month and year of birth
- gender
- ethnic group

### 13.2.2. Cardiovascular, Cancer and significant Medical History

A full medical history will be recorded for each patient at baseline and will include details of all clinically significant current and past cardiovascular medical conditions and a full cancer history. Cancer staging will be assessed according to the eighth edition of the American Joint Commission of Cancer (AJCC) Cancer Staging Manual, published 2016.

Review of other hospital notes (and GP notes) may assist in completing the medical history.

### 13.2.3. Performance Status

ECOG Performance Status grade will be determined at baseline and assessed according to the following criteria:

Grade	ECOG Performance Status
0	Fully active, able to carry on all pre-disease performance without restriction
1	Restricted in physically strenuous activity but ambulatory and able to carry out work of a light or sedentary nature, e.g., light house work, office work
2	Ambulatory and capable of all selfcare but unable to carry out any work activities. Up and about more than 50% of waking hours
3	Capable of only limited selfcare, confined to bed or chair more than 50% of waking hours
4	Completely disabled. Cannot carry on any selfcare. Totally confined to bed or chair
5	Dead

#### 13.2.4. NYHA Class

NYHA Class will be assessed at baseline, in accordance with the following criteria:

Class	Patient Symptoms
I	No limitation of physical activity. Ordinary physical activity does not cause undue fatigue, palpitation, dyspnea (shortness of breath).
II	Slight limitation of physical activity. Comfortable at rest. Ordinary physical activity results in fatigue, palpitation, dyspnea (shortness of breath).
III	Marked limitation of physical activity. Comfortable at rest. Less than ordinary activity causes fatigue, palpitation, or dyspnea.
IV	Unable to carry on any physical activity without discomfort. Symptoms of heart failure at rest. If any physical activity is undertaken, discomfort increases.

